The randomization process involves:

- 1. Treatment assignments will be stored centrally electronically in a secure database at VAPSHCS. Envelopes containing the treatment assignments (hardcopies) will also be pre-generated.
- 2. We will utilize computer-generated permuted-block randomization to achieve roughly balanced groups. We will use random blocks that are not divulged to the research staff involved in recruitment in order to avoid bias in the recruitment process. Randomization will be stratified by MBB block responses (50-79% vs. ≥80%).
- 3. Reminder emails will be sent to the clinical assistant ([name]) and the 2nd interventional spine attending physician the day before the scheduled procedure to remind them that they will need to obtain the randomization allocation on the day of the procedure, prior to the procedure. The 2nd interventional spine attending physician is the second interventional spine attending physician-other than the treating spine provider, who will be in the room during LRFA or simulated LRFA and take part in these procedures. Similar emails will be sent on the morning of the procedure.
- 4. Prior to the lumbar procedure, the clinical assistant and the 2nd interventional spine attending physician will open the envelopes which reveal the procedural and behavioral treatment allocations. A non-blinded research staff member will be present to facilitate this and be aware of the treatment allocations. These assignments contained in the envelopes will direct the 2nd interventional spine attending physician whether to perform a standard LRFA or the simulated LRFA, and whether the participant will receive AcTIVE-CBT or TBSCE. A primary function of the clinical assistant is to make sure that the 2nd interventional spine attending physician knows and performs the allocated treatment on the day of the procedure.

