- 5. On the day of the procedure, once the randomization status is known, the non-blinded research staff member and the PI, [name], will communicate regarding the participant's assignment to AcTIVE-CBT or TBSCE. [name] will then place clinical orders in CPRS for telehealth CBT for pain. These orders will specify whether the order is for a brief course of CBT for pain with education and self-directed plan for progression (TBSCE) or an extended course of CBT for pain (AcTIVE-CBT). The non-blinded research staff member will also communicate directly with the treating CBT provider to clarify that the patient is a study participant. The participant will then be scheduled for

the first session of AcTIVE-CBT or TBSCE, which generally will take place within 1-3 weeks of the procedure date whenever possible.

6. On the day of the procedure, prior to revealing each participant's randomization assignment, we will ensure that we have completed the following aspects of data collection and/or report forms: participant contact Information, the Screening Log (described further below) Informed Consent (Attachment T – Consent, described further below), and baseline questionnaires (the baseline study assessment, pre-randomization, described further below in 'Study Measures'). The Screening Log is a tracking document used for internal study purposes.

Description of LRFA and simulated LRFA control procedures:

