After the treatment allocation for a given participant is known to the clinical assistant and 2nd interventional spine provider, that participant will undergo their lumbar procedure (LRFA or simulated LRFA). Two experienced board-certified pain medicine attending physicians, one of whom is the participant's 'treating' physician who performed the screening MBBs (the 'treating interventional spine provider'), will perform each LRFA procedure. To permit provider blinding, the treating interventional spine provider will place LRFA electrodes at each spinal level to be treated, and will then leave the procedure room, subsequently remaining blinded to allocation. The 2nd interventional spine attending physician (unblinded, not involved in data collection or further care of the participant) will then administer the allocated LRFA treatment or simulated control. For the LRFA group, this involves making a radiofrequency lesion, repositioning the electrode, and making a 2nd RFA lesion, at each medial branch target. For the simulated LRFA group, this involves the placement of electrodes as would normally be done during LRFA, but without making RFA lesions.

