The LRFA technique to be used in this research is consistent with current practices among our VAPSHCS LRFA providers and with the highest clinical standards available, including those detailed in the Spinal Intervention Society Practice Guidelines for Spinal Diagnostic and Treatment Procedures, 2nd edition. Briefly, LRFA involves initially positioning a spinal needle at each 'facet nerve' (medial branch of the dorsal ramus) that will be ablated, in the same manner in which medial branch blocks are typically performed, and administering local anesthetic to the nerve and the immediately surrounding muscles, covering a volume consistent with the expected size of the region to be ablated. The needle is then left in place, serving as a pointer to the nerve target site. A radiofrequency electrode is then placed along the course of the medial branch, using a fluoroscopic declined view approach with cross-table obliguity as needed to achieve electrode placement parallel to the medial branch, to the target point marked by the spinal needle tip. Once the electrode is positioned, sensory stimulation is performed at 50 Hz up to 1 millivolt until the patient reports axial and no extremity sensation to further confirm appropriate location of the electrode. The intensity of sensory stimulation where the patient reports sensation will be noted by the clinical assistant and 2nd interventional spine attending physician. Motor stimulation is performed at 2 Hz up to 4 volts (but typically no more than 2 volts) to confirm that there is no motor stimulation of the ventral nerve root causing muscle contraction. If there is motor stimulation of the ventral nerve root, the electrode is repositioned and the stimulation sequence is repeated until the correct electrode position is confirmed. If unable to achieve sensory stimulation, a lesion would not be attempted at that level. Once the electrode is in correct position and stimulation testing completed, a lesion is generated by raising the temperature at about 1°C per second, from 37°C to an operating temperature between 80°C and 85°C, which is maintained for 90 seconds. The electrode will then be repositioned slightly by withdrawing or repositioning parallel to the 1st ablation site, or by rotating the electrode, and a 2nd lesion will be made. If at any time during the raising of the temperature, or during the coagulation, the patient reports adverse sensations, the generator will be immediately turned off and the sensation evaluated. Depending on provider preference as part of routine clinical care, local corticosteroid injections may be used to decrease the likelihood and/or severity of a post-LRFA 'neuritis', worsening of back pain that can be due to the nerve ablation/lesioning itself. This process is then repeated for each medial branch nerve that is targeted (typically 2 or more medial branches per LRFA procedure).

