
Simulated LRFA with targeted steroid injections technique:

The simulated LRFA control will be performed in an identical fashion to LRFA as above, except that 1) after electrode positioning, a neurodestructive lesion is not made; 2) a targeted corticosteroid injection will be administered at each targeted medial branch prior to the 1st *simulated* lesioning; 3) a prerecorded audio recording of the procedure will be played by the clinical assistant (out of view of the patient, immediately adjacent to the RFA machine) in order to simulate the beeping and other sounds of the machine and to ensure the appropriate length of the simulated procedure, and 4) the 2nd interventional spine attending physician will turn on sensory stimulation for a short period of at least 3 seconds towards the end of the simulated lesion time, maintaining stimulation intensity no higher than the level where sensory input was initially noted by the patient during testing. The electrode will remain in place for the full 90 seconds that lesioning would normally require, but without heat application. The electrode will then be repositioned to simulate a second lesion, also of duration 90 seconds. This process would then be repeated for each medial branch nerve that is targeted (2 or more medial branches per simulated LRFA procedure). Targeted corticosteroid injections will consist of a total injectate quantity per patient not to exceed the equivalent of 40-80 mg triamcinolone, divided equally among medial branch sites to be targeted. Lower doses of corticosteroid may be used as per the providers' clinical discretion.

Description of AcTIVE CBT vs. TBSCE CBT treatments

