- iii. Participants who do wear their Fitbit unit on at least 3 of 7 days during the test period, for 6 hours at least each day during the participant's regular waking hours will be classified as being 'Fitbit-complaint'. Participants who do NOT wear their Fitbit unit on at least 3 of 7 days during the test period, for 6 hours at least each day during the participant's regular waking hours will be classified as 'non-Fitbit compliant'.
- iv. Participants who cannot be contacted at least once during the run-in period will be considered to have failed the run-period. They will be excluded from study participation and will not be randomized.

D. Reassessment of study criteria on the day of randomization (Visit 2):

- i. Initial Screening Criteria will be repeated, as per Table 4 (but not including MBBs). Individuals who no longer meet screening criteria will not be randomized and will not be followed further as part of the study.
- ii. Randomization will take place as described further below.
- iii. The lumbar procedure (LRFA or simulated LRFA) will be performed as per the processes described below.
- iv. Subjects will be given a 2nd study participation pledge form. This version of the pledge form will include the items listed on the 1st pledge form, without information pertinent to the run-in period, but will also include additional details that are specific to each participant's CBT allocation (AcTIVE-CBT vs. TBSCE). Specifically, the AcTIVE-CBT pledge form will encourage the participant to use their Fitbit, and try to gradually increase their daily walking while in the study (Attachment O Pledge Visit 2 Extended). As previously, subjects will have a chance to read the pledge and ask questions, and confirm verbally that they understand the pledge and agree to its content. The participant can keep the pledge form. TBSCE participants will also read a pledge form (Attachment N Pledge Visit 2 Brief), which is the same as (Attachment O Pledge Visit 2 Extended), except it does not specifically encourage active Fitbit engagement, and recommends against using the Fitbit Group or Friend functions.
- v. At the time the 2nd study pledge form is provided by a research staff member, the staff member will will ask the "Post-procedure questions". These involve 1-4 questions, which inquire about the participant's immediate impression of whether they received LRFA, or simulated LRFA.
- E. Approach Letters.

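### The CBT allocation is disclosed before the procedure to two people with no stated use for it, and the LRFA guess is collected with the CBT-specific pledge in no fixed order: an avoidable, probably small, route for bias

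*Combined protocol and SAP*

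**What the plan says.** **Disclosure before the procedure.** In section 5.1, Randomization, item 4, the clinical assistant and the 2nd attending "will open the envelopes which reveal the procedural and behavioral treatment allocations". The contents tell the 2nd attending which procedure to perform "and whether the participant will receive AcTIVE-CBT or TBSCE". A non-blinded research staff member is present. The description of the LRFA and simulated LRFA procedures confirms the sequence. "After the treatment allocation for a given participant is known to the clinical assistant and 2nd interventional spine provider", the participant goes on to the procedure, in which the 2nd attending delivers the lesion or the simulation.

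**Who acts on the CBT arm.** Under item 5, the non-blinded staff member informs the PI, who orders the CBT that day. The first CBT session follows, "which generally will take place within 1-3 weeks of the procedure date whenever possible". The 2nd attending is described as "unblinded, not involved in data collection or further care of the participant".

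**Room for choice.** For LRFA the protocol says: "Depending on provider preference as part of routine clinical care, local corticosteroid injections may be used". For the simulated procedure it says: "Lower doses of corticosteroid may be used as per the providers' clinical discretion".

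**The guess.** Section 5.2 D (iv) has the participant given a second pledge form after the procedure, in an extended or a brief version according to CBT arm. Item (v) places the one to four questions on perceived procedure "At the time the 2nd study pledge form is provided by a research staff member". Neither item says which comes first.

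**The concern.** Two people who are about to deliver, or help deliver, one factor of a 2 x 2 trial learn the allocation on the other factor without needing it. The 2nd attending retains some discretion and works with a patient who is not under general anesthesia and who reports sensations. If conduct or remarks did differ by CBT arm, the difference would enter the LRFA by AcTIVE-CBT interaction. Section 5.6 uses the size of that interaction, relative to the main effects, to choose the comparisons on which the future trial's sample size will rest.

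The guess is a separate matter. A participant who has just been handed the extended pledge may suppose that the more intensive CBT goes with the real procedure, and answer accordingly. The recorded guess would then partly reflect CBT arm. The protocol already treats cues of this kind as worth controlling: it uses neutral names for the two CBT programmes and does not tell participants which is the control.

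**Working it through.** The plan states no figure on this point, so the check is mainly a reading of the text. A short illustration of scale follows.

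**1. Is the early CBT disclosure needed?** Item 4 gives the CBT arm to the assistant and the 2nd attending. Item 5 assigns all CBT actions to the PI and the non-blinded staff member. The procedure description excludes the 2nd attending from later care. No section gives either envelope-opener a task that depends on the CBT arm.

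**2. Is the guess protected from the CBT arm?** The pledge in 5.2 D (iv) is CBT-specific, and the questions in (v) accompany it. No section places the questions first or delays disclosure of the CBT arm until they are answered.

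**3. Scale for the guess.** Inputs: the target of 20 completers (sections 5.1 and 5.6), taken as 10 per procedural arm and 5 per cell. Assumptions: no don't-know answers, a 0.5 probability of guessing LRFA without any cue, and a shift d of 0.1 to 0.3 in that probability once the CBT arm is known. None of these assumptions comes from the documents. With p the proportion guessing correctly, the Bang index in one procedural arm is 2p - 1.

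- Only AcTIVE-CBT shifts guesses, 5/5 CBT split, LRFA arm: 2 x [5(0.5 + d) + 5(0.5)]/10 - 1 = d, so +0.10 to +0.30. In the simulated arm the sign reverses: -0.10 to -0.30.
- The two CBT arms shift guesses equally in opposite directions, 5/5 split: 2 x [5(0.5 + d) + 5(0.5 - d)]/10 - 1 = 0.
- The same with a 6/4 split: 2 x [6(0.5 + d) + 4(0.5 - d)]/10 - 1 = 0.4d, so 0.04 to 0.12.
- Precision: at p = 0.5 the index has variance 1/n, so the 95% half-width at n = 10 is 1.96 x sqrt(1/10) = 0.62.

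Even the largest of these shifts lies well inside the sampling error, so the pilot's data could not show afterwards whether it had happened.

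**4. Precision of the interaction.** With 5 per cell and outcome standard deviation SD, a main effect (10 vs 10) has standard error SD x sqrt(1/10 + 1/10) = 0.45 SD. The interaction, as a difference of differences, has SD x sqrt(4/5) = 0.89 SD. Any conduct that varied by CBT arm would fall on the less precise contrast. This says where a bias would land, not that one exists.

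**The case against.** A reader might infer from the two facts that CBT allocation leaks into the procedure and biases the interaction, or that the procedural blind is broken. The documents support neither reading.

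- **Conduct.** Nothing suggests that knowing the CBT arm would change steroid use or behaviour. The discretion is tied to routine care and clinical judgement and exists whether or not the CBT arm is known. Much of the simulated procedure is scripted: timing, repositioning, recording and stimulation.
- **Operators.** The treating provider places the electrodes and is not listed among those who open the envelopes. The 2nd attending collects no data and gives no further care.
- **Guess.** The CBT arm carries no true information about the procedural arm, so a participant can be misled but not unblinded. Consent presents all treatments as active and the two randomizations as separate 50% chances.
- **Use of the guess.** Section 5.5 lists the Bang index but does not say that it is built from these questions, and section 5.6 uses no blinding measure in the analysis. Participants know their CBT arm once treatment starts, so only the immediate guess can be protected.
- **Cost of separating the reveals.** Two people now open the envelopes with a third present. A CBT envelope opened later by one person who already knows the procedural arm would be a weaker control unless the opening is witnessed or logged.

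All of this stands as a limit on the consequence. It does not supply a reason for the early CBT disclosure or a stated order for the guess, and the last item is met by the form of the fix.

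**Conclusion.** The point holds as an inexpensive improvement to trial conduct. The protocol discloses the CBT arm before the procedure to two people with no stated use for it, and it collects the immediate LRFA guess alongside CBT-specific material without fixing the order. The better-supported consequence is a possible shift in that guess. An effect on procedural conduct is more speculative.

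The procedure applies to every randomized participant, but that counts exposure and is not evidence of bias. The size cannot be derived from the documents and is probably small. The 0.10 to 0.30 movement in the Bang index rests wholly on the assumed one-sided shifts, on equal splits, and on the unstated premise that these questions feed the index. Under symmetric shifts and a 5/5 split it is zero. In a pilot that reports effect sizes this is a minor matter, but the remedy is prevention, since the data could not reveal the problem later.

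**What to change.** 1. **Section 5.2 D (iv-v):** state that the post-procedure questions are asked and recorded before the CBT arm is disclosed to the participant and before the CBT-specific pledge is given.
2. **Section 5.1, Randomization, item 4:** put the procedural and CBT allocations in separate envelopes, or use separate reveals from the central database in item 1. The clinical assistant and the 2nd attending open only the procedural allocation. The non-blinded research staff member opens the CBT allocation after the procedure and after the guess is recorded. That opening is witnessed or time-logged and checked against the central list.
3. **Item 5:** the PI's same-day CBT order follows the second reveal.

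The cost is one more envelope per participant, a fixed order for two same-day steps, and a logged second reveal. No extra staff, visits or analyses are needed, and no change to treatment is implied.

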aining Gains and Coping with cks 60 min. session by ilitation psychologist	 Reading Assignments: Chapter 9 (Effective Problem Solving) Chapter 10 (The End of The Beginning) Topics: Setting Goals Applying your coping skills to problems Relapse Prevention Coping with Pain During Flare-Ups
	leep 60 min. session by ilitation psychologist aining Gains and Coping with cks 60 min. session by

the changes made are substantive.

Blinding Strategy:

Blinding with respect to the lumbar procedures (LRFA vs. simulated LRFA):

- 1. Participants and treating interventional spine providers will be blinded to the status of LRFA vs. simulated LRFA. The PI [name] and [name] will not be blinded, since they are the overseeing study clinicians. Further details are provided below in Table 2.
- 2. For blinding purposes, both LRFA and simulated LRFA will be performed in an identical fashion with the exception of medial branch lesioning, which will not be done in the simulated LRFA group, as described above. Duration and sounds of both the LRFA and simulated LRFA procedures will be similar. Both LRFA and simulated LRFA will apply all safety precautions normally used in our facility such as not using general anesthesia, and the use of both sensory and motor stimulation to avoid incorrect electrode placement (described further below).

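### The 90 seconds set for each simulated lesion covers only the hold and leaves out the 43–48 second temperature ramp of a real lesion

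*Combined protocol and SAP*

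**What the plan says.** All the relevant text is in section 5.1 of the combined protocol and SAP.

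- **LRFA Technique.** For the real procedure, "a lesion is generated by raising the temperature at about 1°C per second", and the temperature goes "from 37°C to an operating temperature between 80°C and 85°C, which is maintained for 90 seconds". The electrode is then moved slightly, a second lesion is made, and the process is repeated for each targeted branch. The stopping rule for adverse sensations names the heating phase and the coagulation phase separately.
- **Simulated LRFA technique.** "The simulated LRFA control will be performed in an identical fashion to LRFA as above", apart from four listed exceptions: no lesion, a steroid injection before the first simulated lesion, an audio recording, and a brief sensory stimulation. On time it says: "The electrode will remain in place for the full 90 seconds that lesioning would normally require, but without heat application". It continues: "The electrode will then be repositioned to simulate a second lesion, also of duration 90 seconds". The recording is there partly "to ensure the appropriate length of the simulated procedure".
- **Blinding Strategy.** Item 2 promises: "Duration and sounds of both the LRFA and simulated LRFA procedures will be similar". Item 3 has the recording played whenever real lesioning would be taking place. Item 4 lists the measures meant to stop patients inferring their arm from sounds or length. Item 4.ii repeats the 90 seconds as one of those measures, and item 4.iii provides for the recording to be pre-tested before the first randomization.

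**The concern.** The simulated-technique text presents 90 seconds as the whole time a real lesion takes. By the LRFA Technique text it is only the second of two phases. The shorter time is not among the four listed exceptions to identical conduct, so the section contradicts itself as well as its own heating parameters.

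Participant blinding to the procedure is at stake. The primary outcome, the Roland-Morris Disability Questionnaire, is patient-reported, and duration is one of the cues that the plan sets out to equalise. An operator who follows the written 90 s would make every simulated lesion about a third shorter than a real one. The recording does not settle the matter, because its running time is not given. If it covers ramp plus hold, it conflicts with the 90 s text and nothing says which governs. If it runs 90 s, it omits the ramp too.

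**Working it through.** **Inputs (section 5.1)**

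- Ramp rate: about 1°C per second (LRFA Technique)
- Start temperature 37°C; operating temperature 80–85°C (LRFA Technique)
- Hold at operating temperature: 90 s (LRFA Technique)
- Simulated lesion: 90 s, first and second alike (simulated technique; Blinding Strategy item 4.ii)
- Two lesions per branch; "2 or more medial branches per simulated LRFA procedure"

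**Can the plan's 90 s be reproduced?** Only by taking the hold alone. If 90 s were the whole cycle, the hold would be 90 − 43 = 47 s (to 80°C) or 90 − 48 = 42 s (to 85°C), which contradicts the stated 90 s hold.

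**Real lesion time** = (operating temperature − 37) / ramp rate + hold

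| | To 80°C | To 85°C |
|---|---|---|
| Ramp at 1°C/s | 80 − 37 = 43 s | 85 − 37 = 48 s |
| Real lesion | 43 + 90 = 133 s | 48 + 90 = 138 s |
| Simulated lesion | 90 s | 90 s |
| Shortfall | 43 s (43/133 = 32%) | 48 s (48/138 = 35%) |

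**Sensitivity to the approximate ramp rate** (0.8–1.2°C/s is my assumption)

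- Shortest ramp: 43/1.2 = 35.8 s; real lesion 125.8 s; shortfall 35.8/125.8 = 28%.
- Longest ramp: 48/0.8 = 60 s; real lesion 150 s; shortfall 60/150 = 40%.

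**Lesion time at the minimum of two branches** (2 × 2 = 4 lesions, made one after another; simulated 4 × 90 = 360 s)

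- Every lesion ramps from 37°C: 4 × 133 = 532 s to 4 × 138 = 552 s, so 172–192 s short.
- Only the first lesion at each branch ramps: 2 × (133 + 90) = 446 s to 2 × (138 + 90) = 456 s, so 86–96 s short (86/446 = 19%; 96/456 = 21%).
- The recording governs and already includes the ramp: no shortfall.

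These are lesion times only. The control-arm steroid injection takes an unstated time, so no whole-procedure difference can be calculated.

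**The case against.** The strongest reply is that the plan has a second control on duration. The recording is described as one of an LRFA procedure, is meant to secure the right length, and is played whenever lesioning would occur. A recording of a real procedure could well contain the ramp, and then no participant would experience a shortfall. This stands as a limit on the consequence: the error is shown in the text, not in the procedure as delivered. It does not rescue the text, which would then conflict with the recording.

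It can also be said that 90 s is shorthand for the hold, or a floor against early withdrawal, with identical conduct implying the ramp. That reading does not survive the sentence giving the second simulated lesion a duration of 90 seconds, or the statement that 90 s is all that lesioning normally needs.

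Other points reduce the importance and are accepted:

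- Participants have had no prior LRFA and so have no personal reference for its length.
- Procedure length already varies with the number of levels, with unilateral or bilateral treatment, and with repositioning.
- The injection at each branch offsets an unknown part of the gap, although steroid is also allowed in the LRFA arm at the provider's preference.
- The plan promises similar duration, not equal duration.
- The treating provider places all electrodes before leaving, so lesions at different branches might be made together. The two-branch totals would then be smaller; the per-lesion figure would not change.

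The post-procedure questions at Visit 2 (section 5.2) and the Bang Blinding Index (section 5.5) would detect failed blinding, but only afterwards.

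**Conclusion.** The concern holds: the 90 s figure is wrong as a statement of full lesion time. On the plan's own parameters a real lesion takes about 133–138 s, so a simulated lesion run to the written time is 43–48 s, or 32–35%, too short. That result needs only the stated ramp rate, temperatures and hold. For the second lesion it also assumes a ramp from 37°C, which the text implies but does not state. The two-branch totals rest further on lesions being made in sequence.

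Severity is minor. This is a correction to blinding fidelity, and the stated intent to match the arms is clear. No difference in whole-procedure length, no unblinding and no bias in the primary outcome is shown. Sample size and analysis are not affected.

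**What to change.** In the simulated LRFA technique text of section 5.1, replace both 90-second statements with wording such as:

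> *Without heat, the electrode stays in position for as long as a real lesion takes (temperature ramp plus 90-second hold). It is then moved, and a second lesion is simulated for as long as a real second lesion takes. The recording runs for these times and determines when each simulated lesion ends.*

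Make the matching change in Blinding Strategy item 4.ii. On the current parameters the time is about 133–138 s per lesion. The sponsor should confirm this, including whether the second real lesion also ramps from 37°C. Check the recording's length against it in the pre-test planned in item 4.iii before letting the recording govern. Keep the brief sensory stimulation near the end of each simulated lesion; a single defined lesion time also settles when that falls.

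The cost is a text edit in two places, plus re-timing of the audio file only if it is shorter than ramp plus hold. Control participants would have up to 43–48 s more unheated electrode time per simulated lesion (up to 172–192 s over two branches), with no treatment benefit to them. No extra staff or procedure is needed. If the recording already covers ramp plus hold, only the text changes.
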